9.0 Procedures Involved

9.1 Describe and explain the study design.

Title: SGB CA Study

We aim to conduct a randomized, single-site, sham-control clinical trial of SGB on VMS in 36 women with breast cancer on anti-estrogen therapy (18 per group). We will need to screen and enroll approximately 50 women to randomize 36 women. Some women may not qualify due to insufficient number of hot flashes or there may be some withdrawals. The primary entry criterion will be 28 or more moderate to very severe hot flashes per week. VMS will be measured by self-report on a written daily dairy over a 6-month period. Secondary outcomes include changes in mood, sleep, quality of life, memory performance with neurocognitive testing, and objective hot flashes measured by ambulatory monitoring (skin-conductance temperature monitoring) for 24 hours at baseline, three months and six months.

Randomization and Masking Procedures A computer-generated 1:1 block randomization scheme will be used to assign participants to receive either a SGB with bupivacaine or a sham injection with saline. Randomization will be performed by the injectionist immediately before the injection procedure by opening an opaque envelope to reveal the participant number and group assignment printed on an index card. Randomization assignment will be kept under lock and key. Participants and all other study personnel, including those who will perform follow-up evaluations, will be blinded to group assignment. The injectionist will not have access to the written VMS diaries until the conclusion of the study.

9.2 Provide a description of all research procedures being performed and when they are performed, including procedures being performed to monitor subjects for safety or minimize risks.

Screening Visit 1

Recording of Hot Flashes

After the participant has reviewed and signed the consent form, they will be interviewed to determine if they are a candidate for the study. We will ask them to provide information about themselves and their medical history. A member of the study team will administer the Depression Anxiety and Stress Scale (DASS) to ensure that participants are not suffering from extreme anxiety or depression. If they are found to have any of these conditions and meet the exclusion criterion, they will not qualify for our study and will be referred to a mental health provider.

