Assignment to groups will be done by randomization similar to flipping a coin. They will have a 50% chance of going into either of the two groups. The study will be single blinded. Participants will not know which group they are in and only [name] will know whether they have received the stellate ganglion injection with numbing medication or the sham injection with saline. Since it is unknown how long the effects of the injection on hot flashes lasts, participants will have the option of receiving a second injection after the three month procedures if they notice an increase in the severity or frequency of their hot flashes. They will receive the same injection (bupivacaine or sham) that they got at the beginning of the study.

Before the procedure, a medication line will be inserted into a vein in the arm. An oxygen monitor and blood pressure cuff will also be placed. They will be positioned on their back for this procedure. Their neck will be swabbed with disinfectant to clean the skin, and sterile equipment and technique will be used for the entire of the procedure. With the use of a low dose x-ray machine (fluoroscopy machine) to help guide the injection, a bone in the right side of the neck (C6) will be identified and local anesthesia or numbing medicine (1% lidocaine) will be injected to the skin overlying the bone.

Title: SGB CA Study

For subjects receiving the stellate ganglion injection, a small needle will be placed through the numbed skin on the front of the right side of the neck to make contact with the tissues over the C6 (neck) bone. The correct position of this needle will be confirmed by injecting a small amount of dye that can be seen by [name] under x-ray. Then 10 cc or about 2 teaspoons of 0.5% bupivacaine (numbing medicine) will be injected and the needle will be removed.

In participants put in the sham injection group, the needle will be placed in the superficial tissues overlying the front right neck (C6 bone), just underneath the skin. 5 cc of saline fluid will be injected and the needle will be removed. This procedure will take a few minutes. After it is completed, they will stay in the office for about half an hour for observation. Their blood pressure will be checked.

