A computer-generated 1:1 block randomization scheme will be used to assign participants to receive either a SGB with bupivacaine or a sham injection with saline. Randomization will be performed by [name] immediately before the injection procedure by opening an opaque envelope to reveal the participant number and group assignment printed on an index card. Randomization assignment will be kept under lock and key. Participants and all other study personnel, including those who will perform follow-up evaluations, will be blinded to group assignment. To ensure that [name] knowledge of randomization assignments does not influence study results, he will have no additional follow up or interaction with study participants, unless an adverse event occurs that requires his immediate attention. The study team will be briefed on the types of adverse events that require his attention. [name] will not be involved in the collection of any primary or secondary data outcome.

11.5 Describe how data and specimens will be handled study-wide: see Section 11.0 Data and Specimen Management

11.6 What information will be included in that data or associated with the specimens?

See Section 11.0 Data and Specimen Management

- Where and how data or specimens will be stored?***

See Section 11.0 Data and Specimen Management

- How long the data or specimens will be stored?***

Title: SGB CA Study

Data will be stored indefinitely.

- ***Who (role on the study) will have access to the data or specimens?***

See Section 11.0 Data and Specimen Management

- ***Who (role on the study) is responsible for receipt or transmission of the data or specimens?***

[name] at NU and [name] at UIC are responsible for the receipt or transmission of data. They may designate a member of the research team to transmit data in accordance with NU/UIC IT security policies.

- ***How data and specimens will be transported?***

See Section 11.0 Data and Specimen Management

Provisions to Monitor the Data to Ensure the Safety of Subjects

11.5 Describe:

- ***The plan to periodically evaluate the data collected regarding both harms and benefits to determine whether subjects remain safe. The plan might include establishing a data monitoring committee and a plan for reporting data monitoring committee findings to the IRB and the sponsor.***

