The study team will meet and review all adverse events after five subjects have been randomized and received the SGB procedure or sham. Per NU IRB protocol, all UPIRSO's or PRNCs will be reported as soon as the PI becomes aware of it. As the PI is the injectionist, the likelihood of missing a UPIRSO is highly unlikely. If no SAEs/UPIRSO's are observed, the team will meet again after 10 subjects have been randomized. No UPIRSOs or SAEs have occurred in previous studies.

- ***What data are reviewed, including safety data, untoward events, and efficacy data?***

Participants who undergo the SGB with bupivacaine will experience a temporary sympathetic block of the right upper extremity and right face. Efficacy of the SGB will be confirmed by the presence of Horner's syndrome (miosis, abnormal contraction of the pupil; ptosis, drooping upper eyelid; and anhydrosis ,absence of facial sweat) and a temperature increase of the affected extremity, the latter the result of regional venodilation. The temperature of the right upper extremity will be monitored prior to and 30 minutes following the injection to confirm, along with a Horner's syndrome, successful SGB. These events are expected and confirm correct SGB placement. Events outside of those expected are what will be reviewed as stated above. The study team will be trained on the types of study related SAEs or AEs that should immediately be reported to the PI/IRB since they will not have access to the procedures records to maintain the blind.

- ***How the safety information will be collected***

Safety data will be collected with case report forms, at study visits, and by telephone calls with participant.

- ***The frequency of data collection, including when safety data collection starts.***

Title: SGB CA Study

Safety data is collected as soon as the participant agrees to participate and signs the informed consent document.

• ***Who will review the data?***

The PI will review the data with the study coordinator.

• ***The frequency or periodicity of review of cumulative data.***

Efficacy data will be reviewed at the conclusion of the study. Safety data will be reviewed after 5 are randomized, then after 10 are randomized. Thereafter, safety data will be reviewed every 6 months provided that no UPIRSOs are observed in those that have received the study procedure.

• ***The statistical tests for analyzing the safety data to determine whether harm is occurring.***

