12.0 Withdrawal of Subjects*

12.1 Describe anticipated circumstances under which subjects will be withdrawn from the research without their consent, including stopping participation for safety reasons.

The PI can remove subjects from the research study without their approval. Possible reasons for removal include the following: if it appears to be medically harmful to the subject, or if they fail to follow directions for participating in the study, such as taking excluded medication (aspirin, anti-coagulants) prior to the SGB procedure, if it is later discovered that they did not meet the study eligibility requirements, at the discretion of the study doctor or, if the study is canceled.

12.2 Describe any procedures for orderly termination.

A subject who withdraws will be scheduled to return to the research office. At this time, written diaries will be collected and AEs will be assessed, if any. Prior to scheduling the appointment, the subject will be asked if she would like to see the PI. If yes, this will be done on the same visit. If a subject does not wish to return, she will be asked to mail or fax any written diaries. Final payment will be mailed to the subject if compensation has not already been paid out.

12.3 Describe procedures that will be followed when subjects withdraw from the research, including partial withdrawal from procedures with continued data collection.

Subjects only have the option of not participating in the cognition study. All other procedures are required as part of the study. The subject has the option to withdraw if she does not want to participate in the hot flash monitoring, actigraph monitoring and most importantly, maintaining a written diary for the duration of the study.

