23.0 Provisions to Protect the Privacy Interests of Subjects

23.1 *Describe the steps that will be taken to protect subjects' privacy interests.*

"Privacy interest" refers to a person's desire to place limits on with whom they interact or to whom they provide personal information.

Potential subjects do not have to authorize the use or disclosure of their health information; however, they will not be allowed to take part in this research study. They may also revoke authorization for use or disclosure of their health information in writing. Direct personal identifiers will not be used in the database. In addition, unless disclosure of the direct identifier is necessary for review by regulatory authorities or is required by law, access to direct identifiers will be strictly limited to research team delegates of the PI.

23.2 *Describe what steps you will take to make the subjects feel at ease with the research situation in terms of the questions being asked and the procedures being performed. "At ease" does not refer to physical discomfort, but the sense of intrusiveness a subject might experience in response to questions, examinations, and procedures.*

Subjects will be reassured that if there are questions in the surveys that they do not want to answer or if some of the questions make them uncomfortable, they do not have to

Title: SGB CA Study

answer them. In addition, if they have questions or concerns about the study procedures the research team, including the PI, is available to them for the duration of the study . They will be told that they do not have to wait for study related clinic visits to be seen or assessed for any concern.

23.3 *Indicate how the research team is permitted to access any sources of information about the subjects. (E.g., What permission does the research staff have to access medical records or other sensitive information?)*

HIPAA Authorization will be obtained from all research subjects through the consent document. Subjects will give us the permission to use personal health information that includes health information in the medical records and information that can identify them. Personal health information may include the subject's name, address, phone number or social security number. Health information we may collect and use for this research includes:

- All information in a medical record
- Results of physical examinations
- Medical history

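### The rule in 11.4 that the unblinded injectionist has no further contact with participants conflicts with 9.2, 23.2 and, nominally, 12.2, so the self-reported diary is less protected than stated

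*Combined protocol and SAP*

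**What the plan says.** Section 11.4 gives the rule and its single exception: "he will have no additional follow up or interaction with study participants, unless an adverse event occurs". The event must be one that needs him at once. The stated purpose of the rule is to keep his knowledge of the assignments from affecting the results.

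Other sections show who he is. Under 9.1, "Randomization will be performed by the injectionist immediately before the injection procedure", by opening the allocation envelope. The safety-monitoring part of section 11 adds: "As the PI is the injectionist, the likelihood of missing a UPIRSO is highly unlikely".

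Three places describe later contact:

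- **9.2, Visit 3:** "participants will have the option of receiving a second injection after the three month procedures". The option is open to women who find that their hot flashes have become worse. The repeat uses the same assignment as the first injection. Section 28.1 makes one person alone responsible for giving the study drugs.
- **23.2:** for questions or concerns about the procedures, "the research team, including the PI, is available to them for the duration of the study".
- **12.2:** before the withdrawal visit is scheduled, "the subject will be asked if she would like to see the PI".

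The primary endpoint in 8.1 is hot flashes that the woman records on a paper diary throughout the study. Section 11.1 summarises them for Months 1 to 6.

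**The concern.** The diary is the woman's own report. Section 2.2 itself warns that placebo response in hot flash studies can be very high, above 60% in some reports, so the protocol treats this outcome as open to expectation. Someone who knows the allocation can shape expectation in conversation without meaning to, and need not see a diary or collect an outcome to do so. The no-contact rule is the one safeguard aimed at that route.

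If other sections allow the contact, a reader of 11.4 credits the trial with a protection that it does not have. What is at stake is a possible arm-dependent influence on diary reporting. Nothing in the plan would show afterwards whether contact had been unequal between arms.

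**Working it through.** No formula or sample-size figure is involved. The check is to set the passages side by side and see which diary periods each contact can reach.

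**1. Is it the same person throughout?** Names are removed in 11.4 and 28.1. The randomization paragraph in 11.4 runs parallel to the one in 9.1, which says the injectionist opens the envelope, and section 11 says the PI is the injectionist. I therefore read the person in 11.4 and 28.1 as the PI. This is an inference, but a well-supported one.

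**2. Does each contact fall outside the adverse-event exception?**

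| Contact | Source | Limited to adverse events? | Conflict with 11.4 |
|---|---|---|---|
| Second injection | 9.2 with 28.1 | No; prompted by the woman noticing worse symptoms | Direct: both cannot be followed once a second injection is given |
| Availability of the PI | 23.2 | No; covers questions and concerns generally | Direct in wording; no contact is scheduled |
| Meeting at withdrawal | 12.2 | No; offered to a woman who withdraws | Nominal |

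**3. Which diary periods can each contact touch?** There are six monthly periods.

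- Second injection: available only after the three-month procedures, so 6 − 3 = 3 periods remain, Months 4 to 6. It cannot affect Months 1 to 3 or the three-month assessments.
- Availability of the PI: all 6 periods.
- Withdrawal meeting: it takes place on the visit at which the diaries are handed in, so it reaches little or no diary data.

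**4. What does the second injection tell the injectionist?** The option depends on a woman noticing worsening. A woman who attends for it thereby signals to the person who knows her arm that her symptoms have worsened. Section 9.1 withholds the diaries from him until the study ends, but that does not prevent this.

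**5. Which protections are left intact?** None of the three contacts contradicts the following:

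- Participants and all other personnel are blinded (9.1, 11.4).
- The injectionist collects no primary or secondary outcome (11.4).
- He has no diary access until the end of the study (9.1).
- His procedure notes are withheld from the team, and the sham is matched for what the woman sees, hears and feels (9.3).
- Objective hot flashes are scored twice by blinded coders (11.1).

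The last item protects the skin-conductance measure. It does not protect the diary.

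**The case against.** The strongest reply is that the sentence in 11.4 does not promise to blind anyone. It limits one person who is openly unblinded, and the blinding commitment is a separate sentence that nothing contradicts. A reader might infer from the three contacts that the trial's blinding does not exist. The documents do not support that. Contact with someone who knows the allocation is a route by which influence could pass; it does not itself reveal the arm to the woman or to the assessors, and the protections in step 5 remain. This part of the objection stands in full.

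Two other stronger readings also fail:

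- A reader might count all 36 women as exposed through the second injection. Section 9.2 restricts it to women who notice worsening, a subset of unknown size.
- A reader might see the withdrawal meeting as a chance to influence whether a woman stays. Section 12.2 concerns a woman who is withdrawing, and the meeting happens only if she wants it.

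It can also be said that 23.2 is a general reassurance, that many concerns raised under it would be adverse events in any case, and that no passage says the injectionist receives or decides requests for a second injection. Those points are fair, and differential influence by arm is a possibility, not something shown. None of them makes 11.4 compatible with 9.2 and 28.1, or with 23.2 as worded.

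**Conclusion.** The point holds as an internal contradiction with a modest consequence. The no-contact rule cannot be followed as written alongside the second injection and the PI's open availability, and it conflicts nominally with the withdrawal meeting. Protection of the self-reported diary from the unblinded PI is therefore weaker than 11.4 states. The exposure is up to 6 of 6 monthly periods through open access. For women who notice worsening and take a second injection, that route adds exposure in 3 of 6.

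The number of women using either route, and any resulting bias, cannot be estimated from the documents. The conclusion assumes that the removed names in 11.4 and 28.1 are the PI. It makes no claim that participants or assessors become unblinded. The issue is minor, but cheap to correct.

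**What to change.** Reconcile the passages as follows:

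- **11.4:** list the only contacts permitted between the injectionist and a participant after randomization: performing a second injection, using a fixed neutral script, and any adverse event or safety concern.
- **Requests and routine matters:** state that existing blinded staff take second-injection requests, withdrawal visits and non-safety questions. The plan does not now say who receives the requests.
- **12.2 and 23.2:** align the wording with 11.4, keeping access to the PI for safety concerns.
- **Contact log:** record each injectionist contact by study ID, with date and reason. Tabulate by arm only after unblinding, because blinded staff cannot keep a log by arm.

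The second-injection encounter with an unblinded person remains; the script limits what passes in it but does not remove it. The cost is wording in three sections, a short script and a simple log, all with existing staff. The small downside is that women take routine, non-safety questions to blinded staff rather than to the PI.

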12.0 Withdrawal of Subjects*

12.1 Describe anticipated circumstances under which subjects will be withdrawn from the research without their consent, including stopping participation for safety reasons.

The PI can remove subjects from the research study without their approval. Possible reasons for removal include the following: if it appears to be medically harmful to the subject, or if they fail to follow directions for participating in the study, such as taking excluded medication (aspirin, anti-coagulants) prior to the SGB procedure, if it is later discovered that they did not meet the study eligibility requirements, at the discretion of the study doctor or, if the study is canceled.

12.2 Describe any procedures for orderly termination.

A subject who withdraws will be scheduled to return to the research office. At this time, written diaries will be collected and AEs will be assessed, if any. Prior to scheduling the appointment, the subject will be asked if she would like to see the PI. If yes, this will be done on the same visit. If a subject does not wish to return, she will be asked to mail or fax any written diaries. Final payment will be mailed to the subject if compensation has not already been paid out.

12.3 Describe procedures that will be followed when subjects withdraw from the research, including partial withdrawal from procedures with continued data collection.

Subjects only have the option of not participating in the cognition study. All other procedures are required as part of the study. The subject has the option to withdraw if she does not want to participate in the hot flash monitoring, actigraph monitoring and most importantly, maintaining a written diary for the duration of the study.

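### Section 12 lets the unblinded PI remove women after randomisation and provides for no diary or visits afterwards, so primary data that the promised ITT analysis needs can be lost

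*Combined protocol and SAP*

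**What the plan says.** Section 12.1: "The PI can remove subjects from the research study without their approval". The grounds are medical harm, not following directions (the example is taking excluded medication before the procedure), cancellation of the study, and "if it is later discovered that they did not meet the study eligibility requirements, at the discretion of the study doctor". No ground is limited to the time before randomisation.

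Section 12.2: a woman who withdraws returns, or sends in, the diaries she has written, and adverse events are assessed. No later data collection is described.

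Section 12.3, whose template prompt asks about partial withdrawal with continued data collection, answers: "Subjects only have the option of not participating in the cognition study. All other procedures are required as part of the study". A woman who does not want the hot flash monitor, the actigraph or the diary has the option to withdraw.

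Section 11.5 on safety monitoring: "As the PI is the injectionist". Under 9.1 the injectionist opens the allocation envelope and everyone else is blinded.

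Section 8.1 makes the primary endpoint the paper diary for the whole study. Section 11.1 promises ITT analysis of all primary and secondary outcomes by mixed models.

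Three safeguards are written down. Section 9.1: "The injectionist will not have access to the written VMS diaries until the conclusion of the study". Section 11.4 says the injectionist will have "no additional follow up or interaction with study participants, unless an adverse event occurs", and also that he takes no part in collecting any primary or secondary outcome. Section 9.2, however, offers women whose symptoms return the following: "option of receiving a second injection after the three month procedures if they notice an increase in the severity or frequency".

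**The concern.** An ITT analysis needs two things: every randomised woman is analysed in her assigned arm, and her outcome is still collected after she departs from the plan. Section 11.1 promises the first. Section 12 does not provide for the second. If the PI removes a woman because she broke an instruction, or because an eligibility failure comes to light late, the plan as written collects her past diaries and describes nothing further. Removal soon after month 3 would lose up to 3 of the 6 diary months (6 − 3), and earlier removal would lose more.

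The decision also lies with the one person who knows the arm. If removals differed by arm and depended on something the analysis does not contain, the treatment contrast could shift. In a trial with 18 women per arm, each lost record counts.

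**Working it through.** **1. Who decides, and when.** 12.1 names the PI, 11.5 identifies the PI as the injectionist, and 9.1 makes the injectionist the only unblinded person. Randomisation takes place immediately before the injection (9.1), so the medication example, which refers to the time before the procedure, acts mainly before randomisation. Whether it also covers the second injection is not stated. Late-found ineligibility and open discretion can clearly act after randomisation.

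**2. Contact after randomisation.** 11.4 allows contact only for adverse events. But 9.2 offers a second injection to women who notice an increase, and 28.1 makes one person solely responsible for giving the study drugs. The name is removed from the text there; I read it as the injectionist. The second injection is therefore a planned contact that 11.4 does not acknowledge, and it selects women reporting worsening.

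**3. The plan's own power figure.** Section 11.2 states at least 80% power with 18 per group for the Treatment by Time interaction at 0.05. This cannot be reproduced: no effect size, SD, within-woman correlation or dropout rate is given. As a stand-in, I use the difference that a two-sample t-test detects with 18 per arm, two-sided 0.05 and 80% power: d = 0.961 SD.

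**4. Power if removed women are lost, unrelated to outcome.** Noncentrality = d × √(n₁n₂/(n₁ + n₂)), with n₁ + n₂ − 2 degrees of freedom.

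| Women analysed | Noncentrality | Power |
|---|---|---|
| 18 v 18 | 0.961 × √(324/36) = 2.88 | 80.0% |
| 17 v 18 | 0.961 × √(306/35) = 2.84 | 78.8% |
| 16 v 18 | 0.961 × √(288/34) = 2.80 | 77.4% |
| 16 v 16 | 0.961 × √(256/32) = 2.72 | 74.9% |

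These losses are upper bounds, because the t-test ignores earlier diary months that a mixed model would use.

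**5. Bias if removal follows visible worsening.** The inputs here are assumptions: diary values at months 3, 4 and 6 with SD 1 and equal correlations of 0.3 to 0.7, and no true effect. One or two of 18 women, in the SGB arm only, are removed after a rise from month 3 to month 4 and lose month 6. The month-6 contrast is estimated by regressing month 6 on arm and the earlier values in women with month-6 data, then applying the fit to all randomised women. With 4,000 runs per setting:

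- Month 4 in the model: shift within 0.01 SD of zero.
- Month 4 not used, largest risers removed: 0.01 to 0.05 SD towards SGB.
- Month 4 not used, random pick from the half with the larger rise: 0.01 to 0.03 SD.

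A repeat with 10,000 runs gave the same picture within simulation error (0.00 to 0.06 SD with month 4 unused). Against the detectable difference, 0.01/0.961 = 1% and 0.05/0.961 = 5%. Removals from the sham arm would reverse the sign.

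**6. Could the latest month go unused?** It could. 11.1 defines the monthly value as the mean over the 30 days before each visit and has no rule for a month cut short by removal.

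**The case against.** The strongest reply is that the diary is kept daily. A woman who asks for a second injection because she is worse has normally recorded that already, and 12.2 collects those pages. A mixed model that uses them handles loss that depends on recorded values. This stands, and it is why the bias is put at about zero in that case.

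The three safeguards also stand. They limit what the injectionist can know and keep him out of outcome collection. Eligibility is re-checked 24 hours before the procedure (3.2), so late findings should be uncommon. The wording of 12.1 is permissive, and no intention to use it widely is stated.

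A reader might go further and infer a large bias towards SGB. Shifts of 0.14 to 0.16 SD do arise if the two women with the largest rise up to month 6 are removed soon after month 3, but nobody can see that rise at the time. A milder version, a random pick from the half with the larger rise to month 6, needs the same foresight.

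A reader might also cite 12.2, where "the subject will be asked if she would like to see the PI", as a route to removal. That meeting is offered to a woman who is already withdrawing, so it cannot drive her removal. The PI's availability under 23.2 is a general statement about questions and concerns.

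What the reply does not answer is the missing follow-up. Pages already written do not replace the months after removal.

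**Conclusion.** The point holds as a gap in follow-up after removal, with the decision placed in the wrong hands. It would be wrong to read the plan as excluding removed women from the analysis: 11.1 commits to ITT, mixed models use partial records, and no sentence says such women are dropped. Nor do the documents show that the unblinded PI would remove women selectively.

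On the stated assumptions the size is small: bias from about zero to about 0.05 SD, and a power loss of at most 1.2 points (80 − 78.8) for one woman, 2.6 (80 − 77.4) for two and 5.1 (80 − 74.9) for two per arm. The removal rate, SD and correlation are not in the documents, so the true size is unknown. The loss is avoidable at little cost, which makes this a cheap improvement.

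**What to change.** In 12.1 and 12.3, state that after randomisation:

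- a deviation, medication breach or late eligibility finding only postpones or withholds an injection;
- every randomised woman who does not withdraw consent continues the diary to month 6 and attends the month-3 and month-6 visits;
- she may decline the monitor or the actigraph while keeping the diary;
- she is analysed in the arm to which she was randomised.

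Have an existing blinded team member decide any non-safety removal and log its date and reason. The PI keeps authority to withhold an injection for safety. Correct 11.4 to acknowledge the contact at the second injection.

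The cost is a few sentences, a short log and some extra follow-up of women who would otherwise have been removed: up to about 3 diary months and one planned visit each if an injection is withheld after month 3, and longer if earlier. No extra participants are needed.
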